9.2 Serious Adverse Event Reporting Instructions

All reportable serious adverse events must be reported using a web-based Electronic Data Capture (EDC) system being used for this trial. For details about accessing the EDC system and completing the on-line SAE report form, please refer to the CCTG Generic Data Management Guidebook for EDC Studies posted on the CO.26 section of the CCTG website (www.ctg.queensu.ca).

Within 24 hours: Complete preliminary Serious Adverse Event Report and submit to CCTG via EDC system.

Within 10 days: Update Serious Adverse Event Report as much as possible and submit report to CCTG via EDC system.

EDC SAE web application interruption:

In the rare event that internet connectivity to the EDC SAE system is disrupted, please print and complete a paper copy of the SAE Report, available from the trial specific website.

FAX paper SAE Report to:

CO.26 Study Coordinator
Canadian Cancer Trials Group
[contact]

Please use the same timelines for submission as for direct EDC reporting.

Once internet connectivity is restored, the information that was FAXED to CCTG on the paper SAE Report must also be entered by the site into the EDC SAE web application.

Local internet interruption:

If you are unable to access the EDC SAE system, and cannot access a paper copy of the SAE Report from the trial website, please phone the CO.26 trial team [contact]) to obtain a copy of the SAE Report by FAX. Once completed, the report must be FAXED back to CCTG as indicated above. Once internet connectivity is restored, the information that was FAXED to CCTG on the paper SAE Report must also be entered by the site into the EDC SAE web application.

In cases of prolonged internet interruptions, please contact the CCTG Safety Desk for further instructions [contact]).

9.3 Other Protocol Reportable Events – Pregnancy Reporting

9.3.1 Pregnancy Prevention

Women of Childbearing Potential (WOCBP) and males who are enrolled in the trial must have agreed to use contraceptive method(s) as described in Eligibility Criterion 4.1.15. Investigators may wish to additionally advise the female partners of male participants about pregnancy prevention guidelines when appropriate and compliant with local policy.

A highly effective method of contraception is defined as one that results in a low failure rate (i.e. less than 1% per year) when used consistently and correctly. Highly effective methods of contraception are described in the table below. Note that some contraception methods are not considered highly effective (e.g. male or female condom with or without spermicide; female cap, diaphragm, or sponge with or without spermicide; non-copper containing intrauterine device; progestogen-only oral hormonal contraceptive pills where inhibition of ovulation is not the primary mode of action [excluding Cerazette/desogestrel which is considered highly effective]; and triphasic combined oral contraceptive pills).

| Highly Effective* Methods of Contraception | |
|---|---|
| Barrier/Intrauterine Methods | Hormonal Methods |
| 
 • Copper T intrauterine device • Levonorgestrel-releasing intrauterine system (e.g. Mirena®)** | 
 • Etonogestrel implants: e.g. Implanon or Norplan • Intravaginal device: e.g. ethinylestradiol and etonogestrel • Medroxyprogesterone injection: e.g. Depo-Provera • Normal and low dose combined oral contraceptive pill • Norelgestromin/ethinylestradiol transdermal system • Cerazette (desogestrel) |
| 
* Highly effective (i.e. failure rate of <1% per year). ** This is also considered a hormonal method.
 | |

9.3.2 Pregnancy Reporting

If a patient becomes pregnant during the course of the study, the investigational agent should be discontinued immediately.

Pregnancy itself - occurring in female participants, and female partners of male participants - is not regarded as an AE unless there is a suspicion that the IP under study may have interfered with the effectiveness of a contraceptive medication. The outcome of all pregnancies (spontaneous miscarriage, elective termination, ectopic pregnancy, normal birth, or congenital abnormality) should be followed up and documented even if the patient was discontinued from the study.

The investigator is required to report to CCTG any pregnancy occurring in female participants, and female partners of male participants. Pregnancies occurring up to 6 months after the last dose of study treatment must also be reported.

The investigator should report the pregnancy in a timely manner, within 24 hours of learning of the pregnancy using the CCTG Pregnancy Reporting Form available from the trial webpage.

Once informed consent has been obtained, the form should be updated to provide further pregnancy information and to reflect the outcome of the pregnancy. All follow-up reports must be submitted to CCTG in a timely manner. For pregnant partner of trial participant (and pregnant participants, if required by local policy), a copy of the signed signature page of the pregnancy follow-up consent must be submitted to CCTG.

Documents outlined above (including updates) must be sent to the CCTG safety desk [contact]/ [contact]).

If the pregnancy results in death (e.g. spontaneous abortion, stillbirth); is life-threatening; requires inpatient hospitalization or prolongation of existing hospitalization; results in persistent or significant disability/incapacity; is a congenital anomaly/birth defect, then an SAE report must be additionally submitted as described above. Please note, hospitalization for labour/delivery alone does not constitute an 'inpatient hospitalization' for the purposes of pregnancy reporting.

9.4 CCTG Responsibility for Reporting Serious Adverse Events to Health Canada

The CCTG will provide expedited reports of SAEs to Health Canada (Office of Clinical Trials) for those events which meet regulatory requirements for expedited reporting, i.e. events which are BOTH serious AND unexpected, AND which are thought to be related to protocol treatment (or for which a causal relationship with protocol treatment cannot be ruled out).

9.5 CCTG Reporting Responsibility to AstraZeneca

AstraZeneca will be notified of all protocol reportable serious adverse events (as defined in Section 9.1) within one working day of receipt of report at CCTG. CCTG, as sponsor, will determine regulatory reportability in Canada.

AstraZeneca will be notified of all pregnancies and outcomes of pregnancies within 30 days of receipt of the report at CCTG.

9.6 AstraZeneca Reporting Responsibilities

AstraZeneca will report all regulatory reportable serious adverse events from non-CCTG trials (Safety Updates) with durvalumab and tremelimumab to CCTG within the timelines outlined in the contract. CCTG will review these events to determine which meet the criteria (serious, unexpected, drug related) for reporting to CO.26 investigators. AstraZeneca will report these events to Health Canada.

9.7 Reporting Safety Reports to Investigators

CCTG will notify Investigators of all Safety Reports (Serious Adverse Events (SAEs) from this trial and Safety Updates (SUs) from other clinical trials) that are reportable to regulatory authorities in Canada as reported to the CCTG. This includes all serious events that are unexpected and related (i.e. possibly, probably, or definitely) to protocol treatment. The reports will be posted to the CCTG trial CO.26 web-based safety monitoring utility.

Investigators must notify their Research Ethics Boards (REBs) of events which involve corrective action(s) to be taken as a result of the event(s) such as protocol and/or informed consent changes. The date of REB Submission for these SAEs and SUs will need to be entered into the CCTG trial CO.26 web-based safety monitoring utility and documentation of REB submission must be retained in the study binder on site. The REB submission template provided by CCTG can be used to assist with tracking, submission, filing and monitoring.

The submission of events to your ethics board should be done as soon as possible (we suggest within 30 days). REB submissions greater than 90 days from the date of notification will be regarded as delinquent and a major deficiency will be assigned. These safety reports are to be filed in the trial files on site.

10.0 PROTOCOL TREATMENT DISCONTINUATION AND THERAPY AFTER STOPPING

10.1 Criteria for Discontinuing Protocol Treatment

Patients may stop protocol treatment in the following instances:

- Intercurrent illness which would, in the judgement of the investigator, affect assessments of clinical status to a significant degree, and require discontinuation of protocol therapy.
- Unacceptable toxicity as defined in Section 7.0 and Appendix III.
- Tumour progression or disease recurrence as defined in Section 8.0.
- Request by the patient.

Efforts should be made to maintain the investigations schedule and continue follow-up, even if patients discontinue protocol treatment prematurely and/or no longer attend the participating institution.

10.2 Duration of Protocol Treatment

Investigators are encouraged to continue therapy, as appropriate in the absence of unacceptable toxicity, until disease progression has been unequivocally documented. This is particularly important for patients in whom pseudoprogression may have occurred. In patients for whom study therapy is continued beyond the first documentation of objective disease progression (i.e. per RECIST 1.1 criteria) on the basis of clinical benefit, continued follow-up assessments per protocol must also be continued until disease progression has been unequivocally confirmed, either through RECIST 1.1 or Immune-Related Response Criteria (irRC) [Wolchok 2009] (i.e. treatment failure), at which time study therapy should cease.

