5.2 Patient Evaluation Flowsheet: Pre-Treatment, On-Study, and after Protocol Treatment
 For Patients Randomized to Durvalumab and Tremelimumab (Arm 2)

| Required Investigations | PRE-STUDY (≤14 days prior to randomization, unless otherwise indicated) | DURING Protocol Treatment Day 1 each cycle, and as clinically indicated (unless otherwise indicated) | AFTER Protocol Treatment is Permanently Discontinued ¹ | | | |
|---|--|---|---|--------------------------|---|---------------------------|
| | | | PRIOR to objective disease progression | | AFTER objective disease progression | |
| | | | 4 weeks after end of last cycle date | Every 4 weeks thereafter | 4 weeks after end of last cycle date ¹ | Every 12 weeks thereafter |
| History and Physical Exam² | | | | | | |
| Including: height (baseline only), weight, ECOG performance status, clinical tumour measurements (if applicable) | X | X | X | X | X | |
| Vital Signs (blood pressure, heart rate, temperature) | X | X ³ | | | | |
| Concomitant Medications | X | X | X | | X | |
| Overall Survival | | | | | | |
| Survival status assessment | | X | X | X | X | X ⁴ |
| Hematology^{2,5} | | | | | | |
| CBC, differential (including lymphocytes), platelets | X | X ² | X | X | X | X ⁵ |
| Coagulation^{2,5} | | | | | | |
| PTT, PT/INR | X | X ² | X | X | X | X ⁵ |
| Biochemistry^{2,5} | | | | | | |
| Serum Creatinine, Chloride, Sodium, Potassium, Calcium, Magnesium, Bilirubin, ALP, AST and ALT, LDH, Albumin, TSH ⁶ , Amylase, Lipase, Serum CEA | X | X ² | X | X | X | X ⁵ |
| Creatinine Clearance (calculated) | X | as clinically indicated | | | | |
| Glucose | X | as clinically indicated | | | | |
| Radiology⁷ | | | | | | |
| Chest/abdomen/pelvis CT or MRI scan | X ≤ 28 days | X ⁷ Every 8 weeks from randomization until objective disease progression (maintain schedule even if cycles are delayed) | | | | |
| Other scans as necessary to document all measurable and non-measurable disease | X ≤ 28 days | | | | | |
| Other Investigations | | | | | | |
| Pregnancy Test ⁸ | X | | | | | |
| ECG | X | as clinically indicated | | | | |
| Dipstick Urinalysis (including protein, specific gravity, glucose and blood) | X | | | | | |

table continued on next page ...

ADMIN UPDATE #1: 2018-JAN-24

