| 
 All patients will be seen at 4 weeks after the end of the last cycle date. Thereafter, continued follow-up is not required for patients who go off protocol treatment with unequivocal progressive disease, except to document ongoing toxicities (until resolved to < grade 2) and late toxicities (including second malignancies). For patients who go off protocol treatment with CR, PR, or SD ongoing, follow-up will be required every 12 weeks until relapse (see Appendix I for investigations to be performed). Death Report will be required for all patients. Due within 2 weeks of knowledge of death (see Appendix IV - Documentation for Study). Timing of Day 1 Assessments: Pre-treatment blood draws and physical exams may be done one working day prior to treatment if necessary, and when treatment is to begin on a Monday, may be done on the previous Friday (maximum 72 hours prior to treatment). In order to ensure that nadir counts are not missed, every effort should be made to do interim blood draws within 24 hours of the day specified in the protocol. If a patient shows an AST or ALT ≥ 3 x ULN together with total bilirubin ≥ 2 x ULN, refer to Appendix III for further instructions on cases of increases in liver biochemistry and evaluation of Hy's Law. These cases should be reported as SAEs if, after evaluation, they meet the criteria for a Hy's law case or if any of the individual liver test parameters fulfill any of the SAE criteria. Note: Labs do not need to be repeated Day 1, Cycle 1. In order to ensure that nadir counts are not missed, every effort should be made to do interim blood draws within 24 hours prior to the day specified in the protocol. Vital signs are to be monitored before, during, and after the infusion of tremelimumab and durvalumab with assessment of vital signs to be collected ≤ 30 minutes prior to start of infusion then every 30 ± 5 minutes during infusion and observation periods. A 1-hour observation period is recommended after the first infusion of tremelimumab, during which time durvalumab may be administered (see Section 7.1.3). A second 1-hour observation period is recommended after the first infusion of durvalumab. If no clinically significant infusion reactions are observed during or after the first cycle of tremelimumab and durvalumab, subsequent infusion observation periods can be at the Investigator's discretion but are recommended to be of 30 minutes, i.e., 30 minutes after tremelimumab infusion, during durvalumab infusion, and for 30 minutes after durvalumab infusion. For patients who receive only durvalumab, the recommended observation period is 30 minutes after infusion. In the event that patient is unable to attend clinic, post-progression follow-up may be by means of telephone contact. Hematology, Coagulation and Biochemistry investigation to be done after objective progression ONLY if there are ongoing hematologic AEs that are related to protocol treatment. If abnormal, T3 and T4 must be measured. To ensure comparability, scans must identify and report each lesion at baseline and at reassessment during treatment. These scans must be performed using identical technique (i.e. scans performed immediately following bolus contrast administration using a standard volume of contrast, the identical contrast agent, and preferably the same scanner). Tumour evaluations must be consistently performed every 8 weeks (i.e. at 8 weeks, 16 weeks, 24 weeks, 32 weeks etc. from randomization) until objective disease progression is documented (as described in Section 8). Sites should adhere to this calendar-based schedule regardless of any delays in treatment. If a radiology scan is done off schedule, future protocol-required scans should still be performed based on the original schedule, i.e. every 8 weeks counting from randomization (not from the date of the off schedule scan). For women of childbearing potential only. May be urine or serum. Pregnancy test (in women of childbearing potential), as part of Pre-Study Evaluation, may include an ultrasound to rule-out pregnancy. See Section 12.0 and the CO.26 Correlative Studies Laboratory Manual for details. Whole blood, plasma and serum should be obtained as close to the time of objective progression as possible and should be done within 28 days (e.g. at the next clinic visit). Blood for correlatives done within 28 days PRIOR to date of progression does not need to be repeated. Adverse Events to be evaluated using the NCI Common Terminology Criteria for Adverse Events (CTCAE v4.0) (see Appendix V). See Section 7 and Appendix III for additional monitoring of patients with toxicity. Follow every adverse event felt related to study therapy until resolved to ≤ grade 2 – i.e. follow-up every 12 weeks until deterioration to ECOG PS 4 and/or end of life care or until all toxicities thought to be possibly-, probably-, or definitely-related to durvalumab or tremelimumab have resolved, returned to baseline, or been deemed irreversible, whichever is longer. To be completed by patient in clinic. | | | | | | |

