7.1.7 Duration of Therapy

In the absence of unequivocal disease progression, as defined in Section 10.2.5, intolerable toxicity or withdrawal of consent to further participation, patients may continue to receive study treatment of durvalumab and tremelimumab at the discretion of the Investigator.

If, in the opinion of the Investigator, a patient is deriving clinical benefit from study therapy despite the documentation of objective disease progression per RECIST 1.1 criteria, then provided the patient does not have any significant, unacceptable, or irreversible toxicities that indicate that continuing treatment will not further benefit the patient, the patient may remain on study therapy pending their next disease assessment. However, appropriate imaging studies must be repeated within 4-8 weeks to re-assess treatment response. A patient with objective disease progression confirmed on subsequent assessment by either RECIST 1.1 criteria or Immune-Related Response criteria (irRC) as appropriate should be discontinued from the study. Patients should also be discontinued from the study if objective disease progression occurs in a target lesion that has previously shown a confirmed response.

For a complete list of general criteria for stopping study treatment, please see Section 10.0.

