8.2 Response and Evaluation Endpoints

Response and progression will be evaluated in this study using the revised international criteria (1.1) proposed by the RECIST (Response Evaluation Criteria in Solid Tumours) committee as well as the Immune-Related Response Criteria (irRECIST). In the event of disease progression using the RECIST 1.1 criteria (unconfirmed PD (uPD)), investigators should continue treatment, if the patient is clinically stable (i.e. stable performance status and disease related symptoms) until disease progression is confirmed at a subsequent scan at least 4 weeks later (unequivocal confirmed disease progression (cPD)). This is particularly important for patients in whom pseudoprogression may have occurred. Follow up response assessments must be continued until unequivocal disease progression has occurred.

8.2.1 Measurable Disease.

Measurable *tumour lesions* are defined as those that can be accurately measured in at least one dimension (longest diameter to be recorded) as ≥ 20 mm with chest x-ray and as ≥ 10 mm with CT scan or clinical examination. Bone lesions are considered measurable only if assessed by CT scan and have an identifiable soft tissue component that meets these requirements (soft tissue component ≥ 10 mm by CT scan). *Malignant lymph nodes* must be ≥ 15 mm in the short axis to be considered measurable; only the short axis will be measured and followed. All tumour measurements must be recorded in millimetres (or decimal fractions of centimetres). Previously irradiated lesions are not considered measurable unless progression has been documented in the lesion.

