| * Note that these lesions should be recorded under the "Non-Target" lesions table on the CRFs. ** Unequivocal progression in non-measurable lesions will be accepted as disease progression. Note : Patients with a global deterioration of health status requiring discontinuation of treatment without objective evidence of disease progression at that time should be reported as "symptomatic deterioration". This is a reason for stopping therapy, but is NOT objective PD. Every effort should be made to document the objective progression even after discontinuation of treatment. | | | |

8.2.7 *irRECIST Response*

8.2.7.1 *irRECIST - Patients With Measurable Disease*

Table 3: Immune-Related RECIST Criteria (irRECIST) for patients with measurable disease:

| Response | Description of Response | Confirmation by |
|--|---|--|
| Complete remission: irCR | Complete disappearance of all lesions (whether measurable or not, and no new lesions). Patient may have had prior uPD by RECIST 1.1 criteria. | Repeat, consecutive assessment no less than 4 weeks from the date first documented |
| Partial Remission: irPR | Decrease in tumour burden $\geq 30\%$ relative to baseline. Patient may have had prior uPD by RECIST 1.1 criteria. | Consecutive assessment at least 4 weeks after first documentation |
| Stable Disease: irSD | Not meeting criteria for irCR or irPR, in absence of irPD. Patient may have had prior uPD by RECIST 1.1 criteria | |
| Progressive disease: irPD | Increase in tumour burden $\geq 20\%$ relative to nadir (minimum recorded tumour burden) | Confirmation by a repeat, consecutive assessment no less than 4 weeks from the date first documented is required |
| New measurable lesions (i.e. ≥ 10 mm in long axis) | Measured but not incorporated into overall assessment of target lesions. | |
| New, non-measurable lesions | Recorded | |
| unidimensional measurements will be collected per RECIST 1.1 | | |

8.2.7.2 *irRECIST - Patients With Non-Measurable Disease Only*

Table 4: Immune-Related RECIST Criteria (irRECIST) for patients with only non-measurable, evaluable, lesions:

| Response | Description of Response | Confirmation by |
|---|---|--|
| Complete remission: irCR | Complete disappearance of all non-measurable lesions (and no new lesions). Patient may have had prior uPD by RECIST 1.1 criteria. | Repeat, consecutive assessment no less than 4 weeks from the date first documented |

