Progression-Free Survival (PFS) is defined as the time from randomization to the first objective documentation of disease progression or death due to any cause. If a patient has not progressed or died at the time of final analysis, PFS will be censored on the date of the last tumour assessment. This includes patients who are lost to follow-up or have withdrawn consent. All analyses for OS will also be performed for PFS, using similar methodology. A sensitivity analysis of PFS will also be performed where PFS is defined as the time from randomization to the second documentation of unequivocal disease progression in those patients who continued study therapy beyond the first objective documentation of disease progression and with interim CR, PR or SD documented.

Objective Response Rate:

Objective Response Rate (ORR) is defined as the proportion of patients with a documented complete response and partial response based on RECIST 1.1. The primary estimate of ORR will be based on all patients randomized. A Cochran-Mantel-Haenszel test adjusting for the stratification factors (ECOG performance status, site of tumour) at the time of randomization will be used to compare the objective response rates between two arms. A sensitivity analysis of ORR will also be performed where response is defined as the proportion of patients with a documented complete response and partial response based on RECIST 1.1 and/or Immune-Related Response Criteria (irRC) [Wolchok 2009].

Safety Analysis:

All patients who have received at least one dose of protocol treatment will be included in the safety analysis. The incidence of adverse events will be summarized by type of adverse event and severity using the NCI Common Terminology Criteria for Adverse Events. A Fisher's exact test will be used to compare adverse events between the two arms if required.

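### The Arm 2 flowsheet ends scheduled scans at objective progression, while protocol 8.2 and 10.2 require assessments until unequivocal progression, so the post-progression sensitivity analyses in 13.2 may be incomplete

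*Protocol*

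**What the plan says.** **How long to assess.** Protocol 8.2 separates an unconfirmed RECIST 1.1 progression from one confirmed on a scan at least 4 weeks later, and then says "Follow up response assessments must be continued until unequivocal disease progression has occurred". Section 10.2 deals with patients whose therapy goes on "beyond the first documentation of objective disease progression (i.e. per RECIST 1.1 criteria") and requires that "continued follow-up assessments per protocol must also be continued until disease progression has been unequivocally confirmed". Section 7.1.7 adds, for a patient kept on drug after RECIST 1.1 progression, that "appropriate imaging studies must be repeated within 4-8 weeks to re-assess treatment response".

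**The scan calendar.** The Radiology row of the Arm 2 flowsheet (5.2) reads "Every 8 weeks from randomization until objective disease progression (maintain schedule even if cycles are delayed"). Its radiology footnote repeats that end point: "until objective disease progression is documented (as described in Section 8").

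**What the scans feed.** Protocol 13.2 plans a PFS sensitivity analysis that runs to "the second documentation of unequivocal disease progression in those patients who continued study therapy beyond the first objective documentation of disease progression", limited to those with a CR, PR or SD in between. It also plans an ORR sensitivity analysis that counts responses by RECIST 1.1 and/or the immune-related criteria. Table 3 (8.2.7.1) requires an immune-related partial response to be confirmed by "Consecutive assessment at least 4 weeks after first documentation", and has a similar rule for a complete response.

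**The SAP.** Section 7.6.3 limits its PFS sensitivity analyses to the handling of other anti-cancer therapy. Section 7.6.5 uses RECIST 1.1 only.

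**The concern.** The protocol gives two end points for the same scans, and the earlier one is in the table that sites use to book them. A centre working from the flowsheet could stop imaging at the first RECIST 1.1 progression, while a centre working from 8.2 and 10.2 would carry on. Whether a late immune-related response or a second progression is seen, and how it is dated, would then depend partly on the centre. The patients concerned are those the 13.2 sensitivity analyses were written for: people who stay on drug because the first progression may not be real.

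**Working it through.** The plan gives no figure on this point, so the check sets the passages side by side and then follows one patient through them.

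| Place | Patients covered | Imaging ends at | Interval given |
|---|---|---|---|
| 5.2 Radiology row and footnote | Arm 2 | objective progression | every 8 weeks |
| 7.1.7 | on drug after RECIST 1.1 progression | one repeat scan specified | 4 to 8 weeks |
| 8.2 | all | unequivocal (confirmed) progression | none, beyond a minimum of 4 weeks to confirm |
| 10.2 | on drug after first RECIST 1.1 progression | unequivocally confirmed progression | none, refers to the protocol schedule |

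**1. What objective progression means.** Section 10.2 glosses it as RECIST 1.1 progression and contrasts it with unequivocal confirmation. Section 7.1.7 uses it the same way. The flowsheet's own first footnote uses the unequivocal term for patients going off treatment, so the flowsheet uses both terms and its scan rule takes the objective one. The natural reading is that the calendar stops at the RECIST 1.1 progression.

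**2. The cross-references do not settle it.** Section 10.2 relies on the protocol schedule, and the only Arm 2 scan calendar is in 5.2. The 5.2 footnote points to Section 8, where 8.2 states the later end point but no interval. Section 7.1.7 cites a Section 10.2.5, but 10.2 has no numbered subsections.

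**3. One patient followed through.** Take a first progression on the scheduled week 8 scan.
- Repeat scan under 7.1.7: from 8 + 4 = week 12 to 8 + 8 = week 16.
- Suppose it shows an immune-related partial response. Table 3 then needs a consecutive assessment from 12 + 4 = week 16 at the earliest, or from 16 + 4 = week 20 if the repeat was at week 16.
- If the 8-week calendar continued, the first qualifying scan would be at week 16 or week 24 respectively, and later scans would date any second progression.
- On the flowsheet alone, the calendar ended at week 8. There are 0 scheduled scans after the repeat, while durvalumab continues every 28 days under 7.1.1.

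The timings themselves are compatible. A calendar scan 8 weeks after the first progression falls inside the 7.1.7 window and meets the 4-week minimum in 8.2. Only the stated end points conflict.

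**4. Data capture.** In Appendix IV the Arm 2 Treatment Report continues every 4 weeks on treatment, with radiology reports and the tumour measurement worksheet requested if available or applicable. Once treatment stops, the Arm 2 Follow-up Report runs only to objective progression.

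**5. Which analyses depend on these scans.** OS does not use them. RECIST 1.1 PFS ends at the first progression, and RECIST 1.1 response is settled by then. That leaves the two 13.2 sensitivity analyses, neither of which is in the SAP.

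**The case against.** The strongest reply is that the body text already covers these patients. Sections 7.1.7, 8.2 and 10.2 all require imaging after a first RECIST 1.1 progression. The flowsheet does not say that the progression is the first one, and its footnote refers to Section 8, which holds the longer rule. The protocol does not keep the two terms fully apart either: the treatment schema ends durvalumab at objective progression, whereas the 7.1.1 table ends it at unequivocal progression. The flowsheet also allows investigations when clinically indicated, and the Treatment Report gives a route for recording them.

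Much of this stands, and it rules out three stronger readings that a reader might reach.

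- *The two analyses would have no data and should be dropped.* The PFS analysis is limited to patients who continued therapy, the group for whom three sections require imaging. The ORR analysis also counts RECIST 1.1 responses and immune-related responses without earlier progression, and these need no post-progression scan.
- *A response first seen on the repeat scan could never be confirmed.* The flowsheet does not schedule a confirming scan, but 8.2 and 10.2 require further assessment.
- *A head count can be given.* Assuming that 10–30% of about 120 Arm 2 patients stay on drug past first progression gives 12–36. The documents do not support that share. It also counts everyone who stays on drug, whereas the gap concerns only those whose repeat scan does not confirm progression. It is at most an upper bound under the assumption.

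What the reply does not remove is the contradiction. A site that follows the flowsheet as printed departs from 8.2 and 10.2.

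**Conclusion.** This is an internal inconsistency that should be corrected. The 5.2 scan end point differs from that in 8.2 and 10.2, and the single repeat scan in 7.1.7 does not bridge the difference once it fails to confirm progression. The supported consequence is inconsistent collection between sites, so the two 13.2 sensitivity analyses may be incomplete. This rests on two assumptions: that objective progression in 5.2 carries the RECIST 1.1 meaning it has in 7.1.7 and 10.2, and that at least some sites scheduled scans from the flowsheet. The number of patients affected is unknown. The primary OS analysis and the RECIST 1.1 PFS and ORR analyses are not touched. The absence of both analyses from the SAP is a separate and more direct obstacle to their being done.

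**What to change.** - Reconcile the 5.2 Radiology row and its footnote with 7.1.7, 8.2 and 10.2, so that one scan end point is stated for patients who remain on study drug after a first RECIST 1.1 progression. Which end point applies is for the sponsor to decide. Correct the 7.1.7 reference to Section 10.2.5 at the same time.
- Reconcile the SAP with protocol 13.2: either specify the two sensitivity analyses in 7.6.3 and 7.6.5, or record that they are not planned and why.
- In any report of these analyses, state how many patients stayed on drug after a first RECIST 1.1 progression and how completely their later scans were obtained.

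The cost is wording, plus a short completeness table. If the end point in 8.2 and 10.2 is kept, no scans are added beyond those already required. SAP 2.1 records that randomization closed on June 29, 2017, and the protocol text carries an administrative update of 24 January 2018. A wording change may therefore recover few scans, which makes the completeness statement the more useful step.
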